7.6. Product Use

A member of the Medtronic team may set up the BIS™ system and Pulse Oximeter at each participating research site in person or via remote webcam to ensure all equipment is fully functional as needed. Specific instructions to the Site Investigator and staff on system set up and use, sensor application, and data transfer will be provided before subject enrollment.

7.7. Product Training Requirements

Prior to site activation or subsequent involvement in clinical study activities, Medtronic will provide clinical study training relevant and pertinent to the involvement of personnel conducting clinical study activities and investigator responsibilities. Principal Investigators (PI) participating in the clinical study and the associated clinical study staff will receive training on the device and system (including but not limited to device characteristics, storage requirements, warnings, precautions, and contraindications.) It is the responsibility of the PI at each participating site to assure any staff performing tasks related to the clinical trial (e.g., Study Coordinators, Study Nurses, Sub-Investigators, etc.) have been appropriately trained, training documented and included on the Delegated Task List.

7.8. Product Receipt and Tracking

The PI or designee will maintain records of devices/products or products provided by Medtronic free of charge delivery to the study site, e.g., device shipping forms, return forms, eCRFs, source worksheets. The following records will be maintained at a minimum for product delivery, receipt, and tracking at the site: dates, quantities received, lot/serial numbers, disposition of device, and expiration dates, as applicable.

7.9. Product Storage

Devices or products provided by Medtronic free of charge must be stored in a secured area. The method of storage shall prevent the use of devices/products for other applications than mentioned in this Clinical Investigation Plan. In addition, all information for the use, storage, and handling of the device/product, as indicated in the IFU and User Manual, must be taken into account.

7.10. Product Return

All monitors provided by Medtronic free of charge should be returned to Medtronic and documentation of return, e.g., device return forms should be maintained. Devices that are single use provided by Medtronic and used in the study should be discarded and documented as discarded on the device accountability log unless non-functioning. Non-functioning investigational devices must be returned to Medtronic as soon as possible for investigation. Instructions for returning the device will be provided. Unused devices will be returned to Medtronic at the end of the study.

7.11. Product Accountability

Devices/products will be traced during the clinical study by specific serial numbers (or lot numbers) assigned to each device/product. The Investigator is responsible for the maintenance of a Product Accountability as tracked on source worksheets, device shipment/return forms, and device eCRFs. On this

Medtronic Business Restricted

documentation, the receipt, use, return, and disposal of the investigational devices/products shall be documented. At the end of the clinical study, the Principal Investigator or delegate must sign and date the applicable eCRFs.

8. Study Site Requirements

8.1 Investigator / Investigation Study Site Selection

All investigators managing the subject's anesthesia must be qualified practitioners and experienced in the diagnosis and treatment of subjects undergoing anesthesia. All physicians must be trained in the handling of the BIS™ Complete Monitoring System.

The role of the principal investigator is to implement and manage the day-to-day conduct of the clinical investigation as well as ensure data integrity and the rights, safety and well-being of the subjects involved in the clinical investigation.

The principal investigator shall:

- Be qualified by education, training, and experience to assume responsibility for the proper conduct of the clinical investigation
- Be experienced in the field of application and training in the use of the BIS™ Complete Monitoring System
- Disclose potential conflicts of interest, including financial, that interfere with the conduct of the clinical investigation or interpretation of results
- Be able to demonstrate that the proposed investigational study site:
 - Has the required number of eligible subjects needed within the recruitment period
 - Has one or more qualified investigators, a qualified investigational study site team and adequate facilities for the foreseen duration of the clinical investigation

Study site personnel training will be completed and documented prior to participation in this study.

8.2 Study Site Activation

During the activation process (prior to subject enrollment), Medtronic will train study site personnel on the clinical investigation plan, on relevant standards and regulations, informed consent, and on data collection and reporting tools. If new members join the study site team, they will receive training on the applicable study requirements relevant to their role before contributing to the study.

Prior to performing study related activities, all regulatory requirements shall be fulfilled, including, but not limited to the following:

- IRB approval (and voting list, as required by local law) of the current version of the CIP and IC.

Medtronic Business Restricted

- RA approval or notification (as required per local law)
- Fully executed CTA
- Financial disclosure
- CV of investigators and key members of the investigation study site team.
- Documentation of delegated tasks
- Documentation of study training.
- Additional requirements imposed by local regulations, the IRB and RA shall be followed, if appropriate.

In addition, all participating study site staff must be trained on the current version of the CIP as well as on the applicable study requirements depending on their role and must be delegated by the principal investigator to perform study related activities.

Medtronic will provide each study site with documentation of study site/investigator readiness; this letter must be received prior to performing study related activities.

8.3 Role of the Sponsor Representatives

In addition to performing monitoring and auditing activities, sponsor representatives may provide support at the study site as required for the study under supervision of the Principal Investigator, including:

- Provide study training relevant and pertinent to the involvement of personnel conducting study activities and investigator responsibilities
- Technical support at SIV and training cases under the supervision of a study investigator, but no data entry, shall be performed by Medtronic personnel or their representatives at study sites

9. Selection of Subjects

9.1. Study Population

Male and female pediatric subjects between the ages of 4 to 18 years undergoing routine sevoflurane general anesthesia will be enrolled. The first 2 - 4 subjects per each site will be used for training and to check the data quality. After training subjects have been enrolled, randomization will proceed based on the Sponsor's assessment of data quality. The subjects will be recruited at up to 8 Investigational Sites in the U.S. and divided into three age groups:

- 4 to 8 years
- 9 to 12 years
- 13 to 18 years

9.2. Subject Enrollment

Subjects will be enrolled in the study once all eligibility requirements for the study have been met. Subjects who give informed consent for the protocol to undergo screening for eligibility are not considered enrolled and should not be enrolled until the screening is completed as indicated in **Sections 9.3, 9.4 and 10**, and the subject is determined to meet all eligibility criteria.

Study enrollment is accomplished by parent/ guardian signing the informed consent, age-appropriate assent form as required, and successfully passing the study inclusion /exclusion criteria. Subjects who sign informed consent, but are not enrolled, are considered screen failures.

9.3 Inclusion Criteria

- 1) Pediatric Subjects (ASA PS I or II or III) aged 4 years to 18 years scheduled for procedures with sedation where the process of assessment will not interfere with the procedure, progress, or patient care

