Study Design	
This is a multi-center, prospective, observational, non-invasive, randomized controlled study to collect data to compare the performance of standard practice (SP) group with the BIS™ monitoring (BIS) group. Pediatric patients between the ages of 4 to 18 years undergoing routine sevoflurane general anesthesia with an expected maintenance duration of greater than 30 minutes will be recruited. If the maintenance duration is less than 25 minutes, the data will continue to be collected, but will not be included in the data analysis and the subject will be replaced with an additional subject. General surgeries including abdominal, urological, orthopedic, ophthalmological or other procedures approved by the Medtronic study team with an American Society of Anesthesiologists physical status of I - III. Children will be recruited from the preoperative clinic and will be divided into three age groups
 
• 4 to 8 years• 9 to 12 years

Medtronic Business Restricted

- 13 to 18 years

A training group comprising of the first 2 - 4 subjects at each site will be enrolled to train the site team on the new technology and to determine the quality of data collection prior to randomization. Afterward, randomization will proceed based on the Sponsor's assessment of data quality.

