5.2.2. Secondary Endpoint(s)

Additional/Exploratory Endpoints:

- Recovery assessments in patients receiving monitoring compared to standard anesthetic practice (instructions for collection contained in **Study Procedures and Assessments**):
 - Emergence,
 - Emergence is defined as the time when any of the following first occurred:
 - Eyes open spontaneously
 - Crying or phonating
 - Purposeful movements
 - PACU discharge readiness using Modified Aldrete Score
 - Anesthesia Airway Management (AAM) will be noted:
 - Awake and Deep Extubation (endotracheal tube (EET) vs. laryngeal mask airway (LMA)
 - Airway reflexes (e.g., coughing, choking, laryngospasm)

Medtronic Business Restricted

6. Study Design

This is a multi-center, prospective, randomized controlled study to collect data to compare the performance of standard practice (SP) group with the BIS™ monitoring (BIS™) group. Pediatric patients between the ages of 4 to 18 years undergoing routine sevoflurane general anesthesia with an expected surgical procedure duration of 30 minutes or more will be recruited. General surgeries include abdominal, urological, orthopedic, ophthalmological, or other procedures approved by the Medtronic study team with an American Society of Anesthesiologists physical status of I - III. Children will be recruited from the preoperative clinic and will be divided into three age groups:

- 4 to 8 years
- 9 to 12 years
- 13 to 18 years

A training group, comprising of the first 2 - 4 subjects at each site will be enrolled to train the site team on the new technology and to determine the quality of data collection before randomization. Afterward, randomization will proceed based on the Sponsor's assessment of data quality.

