10.9 Surgical Procedure and Data Collection

The surgical procedure will be conducted per Standard of Care (SOC). Subjects are being recruited with a planned maintenance time of 30 minutes or greater. If the subject's maintenance time is less than 25 minutes, the data will continue to be collected, but will not be included in the final data analysis and the subject will be replaced by an additional enrolled subject.

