7.1.3 Analysis Sets

All study subjects (excluding training) that satisfied the inclusion and exclusion criteria will be included in the analysis.

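### The protocol and SAP contradict each other, and themselves, on who is recruited and which randomized children form the primary dataset

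*Protocol*

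**What the plan says.** **Who is recruited.** Section 9.3 and the synopsis hold one inclusion criterion: ASA I to III, age 4 to 18, "scheduled for procedures with sedation where the process of assessment will not interfere with the procedure, progress, or patient care". None of the eleven exclusions adds an agent, general anesthesia or a duration. Section 9.1 describes children "between the ages of 4 to 18 years undergoing routine sevoflurane general anesthesia will be enrolled". Section 9.2 says subjects "should not be enrolled until the screening is completed as indicated in" Sections 9.3, 9.4 and 10.

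**Duration.** Section 10.9 states: "Subjects are being recruited with a planned maintenance time of 30 minutes or greater". The synopsis design row also uses expected maintenance, but as strictly more than 30 minutes. Section 6 describes patients "undergoing routine sevoflurane general anesthesia with an expected surgical procedure duration of 30 minutes or more will be recruited", and SAP section 5 uses that same surgical clock.

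**Who is analyzed.** SAP 7.1.3 states: "All study subjects (excluding training) that satisfied the inclusion and exclusion criteria will be included in the analysis". The synopsis states: "If the maintenance duration is less than 25 minutes, the data will continue to be collected, but will not be included" in the analysis, and Section 10.9 repeats the rule. The protocol also removes and replaces children who need unplanned regional anesthesia or dexmedetomidine (synopsis, Section 10.9.2), and those outside BIS 45 to 60 for more than 35% of maintenance (synopsis, Sections 10.9.3.3 and 14.1). SAP 7.4 sets that last limit at 25%. SAP section 6 replaces *non-qualifying* data sets and SAP 7.9 analyzes *evaluable* data; the SAP defines neither term.

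**The concern.** The primary endpoint is end-tidal sevoflurane during maintenance. The conditions that make a child able to supply it (sevoflurane, general anesthesia, enough maintenance time) belong in the list that screening staff tick. Here they sit in descriptive text, and the duration is measured differently from place to place.

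The larger stake is the primary dataset. If the rule for membership differs between SAP 7.1.3, SAP 7.4 and the protocol, two competent statisticians can lock different datasets from the same trial. Every disputed child is a randomized child, so the choice also affects how far the comparison remains a randomized one. The target of 108 qualifying data sets inherits the ambiguity, because replacement and the end of recruitment depend on which children count.

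**Working it through.** **1. The plan's own sample size.** Inputs from Section 14.2: difference 0.5%, SD 0.5%, two-sided alpha 0.05, more than 80% power, 18 per arm in each of three age groups.

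- Normal approximation: n = 2 × (1.960 + 0.842)² × (0.5/0.5)² = 15.7, so 16 per arm. Power at 18 per arm = Φ(√(18/2) − 1.960) = Φ(1.04) = 0.851.
- Two-sample t-test: 17 per arm is the smallest size reaching 80% (power 0.807); 18 per arm gives 0.830.
- Total: 3 × 36 = 108.

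The stated size reproduces, and nothing in this point changes it.

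**2. The recruitment rule, place by place.**

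| Place | Anesthetic | Minimum duration |
|---|---|---|
| Synopsis criteria, 9.3 | sedation | none |
| 9.1 | sevoflurane general anesthesia | none |
| Synopsis design | sevoflurane general anesthesia | maintenance > 30 min |
| 10.9 | not stated there | maintenance ≥ 30 min |
| 6, SAP 5 | sevoflurane general anesthesia | surgical procedure ≥ 30 min |

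Surgical time and maintenance time are different intervals, so a child can meet one rule and fail the other.

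**3. The same child under each analysis rule.** Take randomized, non-training children who met the criteria in 9.3 and 9.4, each with only the feature shown. For the BIS rows, the protocol's exception for titration on clinical signs is taken not to apply.

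| Child | SAP 7.1.3 | SAP elsewhere | Protocol |
|---|---|---|---|
| Maintenance 22 min | in | not addressed | out |
| Unplanned caudal block | in | not addressed | out |
| Other unplanned regional block | in | not addressed | out under 10.9.2; the synopsis removal names only a caudal block |
| Dexmedetomidine given | in | not addressed | out |
| BIS-guided, out of range 30% of maintenance | in | out (7.4) | in |
| BIS-guided, out of range 40% of maintenance | in | out (7.4) | out |

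For the first four rows, the undefined terms in SAP 6 and 7.9 could be read either way. In the fifth row the SAP removes a child whom the protocol keeps, so the conflict does not run in one direction. Section 10.14.1 adds that data available up to a subject's exit will be used for analysis, without mentioning the removals.

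**4. A partial cause.** The SAP says that it elaborates protocol version 2.0, while the version history runs to 4.1. That history places the move from 25% to 35%, and the change to maintenance duration, in version 3.0. Yet the SAP's sample-size section matches the current Section 14.2, so the SAP is not uniformly out of date.

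**5. What a miscount could cost.** The documents give no rate of disputed children, so this is an assumption shown over a range. Suppose recruitment stops at 18 per arm under the wider rule, and 10%, 20% or 30% are later ruled out without replacement. Rounding down leaves 16, 14 or 12 per arm in an age group, with t-test power of 0.78, 0.72 or 0.65.

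**The case against.** The strongest reply is that the protocol read as a whole does select the right children. Section 9.1 sits in the chapter on selecting subjects and names sevoflurane general anesthesia. Section 9.2 sends screening to Section 10, where 10.9 gives the planned maintenance time and 10.9.2 specifies sevoflurane induction. The protocol also uses *sedation* loosely for anesthetic depth, both in its background account of a sevoflurane trial and in its statistics text. This stands. A reader might infer that the trial is open to sedation-only cases, or that a child booked for a short case would pass the electronic eligibility check. The documents do not support either inference: the eligibility form is not among them, and the 25-minute rule acts on observed maintenance, which nobody knows before randomization. What remains is that Section 9.2 itself ends by making enrollment turn on consent, assent and the inclusion and exclusion criteria, and that Section 10 is a whole procedures chapter rather than a checklist.

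On the analysis set, a reader might infer that the SAP keeps every child the protocol discards. It does not. SAP 7.4 excludes out-of-range children, SAP section 6 rejects some data sets, and Section 14 of the protocol refers data exclusion to a Data Management Plan that is not supplied. But a separate plan does not remove a literal conflict between SAP 7.1.3 and the other texts.

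It is also tempting to size the loss from the surgical durations of the earlier 3-to-18-year cohort tabulated in the protocol. Those are surgery times in tonsillectomy or adenoidectomy patients, with no 30-minute minimum described, so they do not measure this defect.

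**Conclusion.** The point holds as a contradiction between the governing texts that should be resolved before the database is locked. It does not show that eligibility fails to select the intended population.

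Two parts are established from the wording alone. The formal criterion does not match the described population, and the minimum duration uses two clocks. SAP 7.1.3 also conflicts with three protocol removals and with SAP 7.4, while the terms that might reconcile them are undefined. The number of children affected cannot be derived from the documents. The power figures of 0.78 to 0.65 rest on assumed rates of 10% to 30%, and apply only if the count toward 108 and the final analysis follow different rules. They do show how little slack there is: each age group is powered separately, and two children fewer per arm than the planned 18 takes t-test power below 80%.

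**What to change.** - In Section 9.3 and the synopsis, state sevoflurane general anesthesia and one expected-maintenance duration rule. Use the same clock in Section 6 and SAP section 5.
- Update the SAP to the current protocol version.
- Reconcile the passages on regional anesthesia (caudal only or any), dexmedetomidine and the BIS-range limit (25% or 35%). Which rule applies is for the sponsor and its clinical advisers; the documents need to agree.
- Rewrite SAP 7.1.3 to define *evaluable* and *qualifying*, list every removal rule there, and say which children count toward the 108.
- Add a sensitivity analysis of all randomized children with recorded maintenance sevoflurane, including those removed after randomization. Keeping short cases in the primary analysis would reverse a stated protocol rule, so they fit better here.

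The cost is wording in two documents and one extra analysis. The sample-size calculation is unchanged.

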9.4 Exclusion Criteria

1) Has severe contact allergies that may cause a reaction to standard adhesive materials found in pulse oximetry sensors, ECG electrodes, respiration monitor electrodes, or other medical sensors

2) Known neurological disorder (e.g., epilepsy, the presence of a brain tumor, a history of brain surgery, hydrocephalic disorders, depression needing treatment with anti-depressive drugs, a history of brain trauma, hemiplegia, demyelinating disorders, cerebral palsy, congenital anomalies of the brain or spinal cord, or other known neurologic disorders)

3) Severe developmental delay per assessment of investigator or report of parent/guardian

4) Airway abnormalities

5) Pregnancy; subjects of childbearing potential will have a urine screen for pregnancy before surgery

6) If the process of assessment will interfere with the procedure or the progress of the procedure

7) Taking psychoactive medications

8) Taking any medications that may have an impact on the Central Nervous System (CNS)

9) Planned use of any regional anesthesia; a local field block is not included in this exclusion and can be used at the discretion of the anesthesia provider

10) Planned use of dexmedetomidine (Precedex)

11) Refusal to participate in the study

10. Study Procedures

10.1 Schedule of Events

The Flowchart for enrollment and allocation to groups is shown in **Figure 10**. The Schedule of Events, **Table 5**, summarizes the intervals and data collection procedures.

[figure not shown]

Figure 10: Study Flowchart

10.2 Data Collection

Table 5: Data collection and study procedure requirements at subject visits

Study Tasks	Baseline/ Enrollment	Surgical Procedure			PACU/ Discharge
		Randomization	Induction and maintenance	End of Surgery	
Baseline					

Medtronic Business Restricted

Study Tasks	Baseline/ Enrollment	Surgical Procedure			PACU/ Discharge
		Randomization	Induction and maintenance	End of Surgery	
Informed Consent ¹	x				
Inclusion/exclusion criteria review and confirmation of eligibility status	x	x			
Demographics ²	x				
Medical History ³	x				
Pre-operative Vital Signs ³	x				
Procedure					
Randomization (before the procedure for group assignment) ⁴		x			
BIS™ and Nellcor™ sensors placement			x	x	
BIS™, Nellcor™ and other digital data collection			x	x	
Standard surgical procedures			x	x	
ET _{SEVO} concentration and other drug information			x	x	
Cardiovascular Variables ⁵	x		x	x	
Event Markers and Assessments collection ⁶			x	x	
Anesthesia Airway Management ⁶			x	x	
Recovery					
Emergence ⁷				x	x
Incidents of postop nausea and vomiting ⁷				x	x
Vitals ⁷				x	x
Wong-Baker FACES Scale ⁷				x	x
Pediatric Anesthesia Emergence Delirium (PAED) ⁷				x	x
Modified Aldrete Score				x	x

Study Tasks	Baseline/ Enrollment	Surgical Procedure			PACU/ Discharge
		Randomization	Induction and maintenance	End of Surgery	
Time of Readiness for PACU discharge ^{6,7}				X	X
Exit					
Reason for Study Exit ⁸	X	X	X	X	X
Safety					
Adverse Event Assessment ⁹	X		X	X	X
Device Deficiency ⁹			X	X	

- 1) Written informed consent must be obtained before any study-specific evaluations, *Section 10.5*
- 2) Demographic information, including sex, weight, height, age, ethnicity, race, as well as skin tone, will be recorded refer to *Section 10.6*.
- 3) Relevant Medical History, including diagnosis and surgery type, will be collected, *Section 10.7*
- 4) Randomization will be performed before the surgical procedure for group assignment refer to *Section 10.8*.
- 5) Cardiovascular Variables (heart rate [HR]; systolic and diastolic blood pressure [BP] including hypotension; oxygen saturation; and temperature) refer to *Section 10.9*.
- 6) For event markers and assessments, refer to *Section 10.9*
- 7) For recovery data collection, refer to *Sections 10.9*.
- 8) Details are included in *Section 10.14..1*
- 9) Details are included in *Section 12*.

